3.6.3.2 Clinical Laboratory Assessments

A central laboratory designated by the sponsor will be used for all laboratory testing required. Reports from the central laboratory should be filed with the source documents for each subject. The central laboratory will provide laboratory results to the sponsor electronically.

Samples for serum chemistry, hematology, and urinalysis will be obtained at baseline, every 12 months (study months are every 4 weeks which is defined as 28 [-2/+10] days), and at Study Completion or the Early Termination visit as specified in [Table 3.6-1](#). Urine and blood samples may be collected for further evaluation of safety as warranted by the investigator's judgment.

Subjects should be fasting for a minimum of 10 hours prior to any blood draws for assessment of safety, including baseline. If a nonfasting blood sample is initially obtained and the test results possibly impacted, a fasting blood sample should be drawn shortly afterwards and the affected lab test(s) repeated. The laboratory tests to be evaluated in this trial are listed in [Table 3.6.3.2-1](#).

For Study 270, a urine pregnancy test will be performed at baseline, every 3 months, at Study Completion or the Early Termination visit, and at any time at the discretion of the investigator when pregnancy is suspected for all WOCBP (see [Section 5.4](#) for the definition of WOCBP) to confirm that the subject is not pregnant. Any positive urine pregnancy test result will be confirmed by a serum test.

Protocol 31-10-270

Table 3.6.3.2-1 Baseline Clinical Laboratory Assessments	
Hematology: White Blood Cell Count (WBC) with differential Red Blood Cell Count (RBC) Hematocrit Hemoglobin Platelet count Urinalysis Specific gravity pH Glucose Protein Ketones Blood Microscopic exam (performed only if any part of the urinalysis is not negative) Other Urine pregnancy (WOCBP) ^a Serum beta-human chorionic gonadotropin (β -hCG) (WOCBP) ^a Urine drug screen Blood alcohol	Serum Chemistry: Blood Urea Nitrogen (BUN) Creatinine Creatine Phosphokinase (CPK) Aspartate Transaminase (AST or SGOT) Alanine Transaminase (ALT or SGPT) Lactate Dehydrogenase (LDH) Alkaline Phosphatase (ALP) Total Bilirubin Triglycerides Cholesterol (total, low-density lipoprotein [LDL], and high-density lipoprotein [HDL]) Calcium Glucose Hemoglobin A1c ^b Insulin Sodium Potassium Total Protein Uric acid Gamma Glutamyl Transferase (GGT) Prolactin

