### **5.5.2 Clinical Laboratory Tests**

Clinical laboratory tests include serum chemistry analysis, hematology analysis, urinalyses and other lab analysis. The potentially clinically relevant laboratory test abnormalities will be listed by subject and by test for the safety sample, respectively. Criteria for the potentially clinically relevant laboratory test abnormalities per protocol are provided in [Appendix 1](#). Per Hy's law, the subjects with AST or ALT  $\geq 3$  x upper limit of normal value and total bilirubin  $\geq 2$  x upper limit of normal values will be listed as the potential Hy's law cases. The incidences of potentially clinically relevant laboratory tests abnormalities based on the observation from the scheduled and the unscheduled post-baseline visits will be tabulated. In addition, incidence of potentially clinically relevant laboratory tests in potassium ( $\leq 3.0$  mEq/L or  $\geq 5.5$  mEq/L) and neutrophils ( $\leq 1500/\text{mm}^3$ ) per FDA recommendation will be provided. Summary statistics (frequency, mean, standard deviation, minimum, and maximum) for the clinical laboratory measurements at all scheduled visits, and changes from baseline at scheduled visit and last visits will be presented for the safety sample.

If laboratory tests assessments are repeated for the same visit, the last repeated values are used for summary tables. This is accomplished by sorting patient data by visit date and visit time (if applicable) within the same visit identification. If the lab data are recorded as ranges (i.e., including below or above limit of quantification), these data are not

included in the calculations for changes from baseline but included in the calculations for incidence.

The incidence of prolactin level above the upper limit of normal range (potentially clinically relevant change) will be tabulated by gender and the designated visits for the safety sample. The change from baseline in prolactin levels will be presented by gender at scheduled visit and last visit for the safety sample.

Additionally, incidence of treatment-emergent clinically relevant changes in fasting lipid parameters and glucose (as defined in [Table 5.5.2-1](#)) will be summarized for the safety sample.

Table 5.5.2-1 Treatment-emergent Clinically Relevant Changes in Lipids Parameters and Glucose		
Parameters	Baseline	Post-baseline
Total Cholesterol(mg/dL), fasting		
	Normal <200	High >=240

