## Protocol 31-10-270 Statistical Analysis Plan

CT-8.5.2	INCIDENCE OF SERIOUS TREATMENT-EMERGENT ADVERSE EVENTS BY SYSTEM ORGAN CLASS AND MEDDRA PREFERRED TERM
CT-8.5.3	INCIDENCE OF SERIOUS TREATMENT-EMERGENT ADVERSE EVENTS BY SYSTEM ORGAN CLASS AND MEDDRA PREFERRED TERM AND SEVERITY
CT-8.5.4	OCCURRENCES (NUMBER OF EVENTS) OF SERIOUS TREATMENT-EMERGENT ADVERSE EVENTS BY SYSTEM ORGAN CLASS AND MEDDRA PREFERRED TERM
CT-8.5.5	OCCURRENCES (NUMBER OF EVENTS) OF POTENTIALLY DRUG-RELATED SERIOUS TREATMENT-EMERGENT ADVERSE EVENTS BY SYSTEM ORGAN CLASS AND MEDDRA PREFERRED TERM
CT-8.6.1	INCIDENCE OF TREATMENT-EMERGENT ADVERSE EVENTS RESULTING IN DISCONTINUATIONS OF STUDY MEDICATION BY SYSTEM ORGAN CLASS
CT-8.6.2	INCIDENCE OF TREATMENT-EMERGENT ADVERSE EVENTS RESULTING IN DISCONTINUATIONS OF STUDY MEDICATION BY SYSTEM ORGAN CLASS AND MEDDRA PREFERRED TERM
CT-8.6.3	INCIDENCE OF TREATMENT-EMERGENT ADVERSE EVENTS RESULTING IN DISCONTINUATIONS OF STUDY MEDICATION BY SYSTEM ORGAN CLASS, MEDDRA PREFERRED TERM AND SEVERITY
CT-9.1	LISTING OF DEATHS
CT-9.2	LISTING OF SERIOUS ADVERSE EVENTS
CT-9.3	LISTING OF DISCONTINUATIONS DUE TO ADVERSE EVENTS
CT-9.4	LISTING OF ADVERSE EVENTS RELATED TO SUICIDAL IDEATION/SUICIDE
CT-9.5	LISTING OF POTENTIAL HY'S LAW CASES
CT-10.1	LISTING OF LABORATORY VALUES OF POTENTIAL CLINICAL RELEVANCE BY SUBJECT
CT-10.2	LISTING OF LABORATORY VALUES OF POTENTIAL CLINICAL RELEVANCE BY TEST
CT-10.3	CRITERIA FOR LABORATORY VALUES OF POTENTIAL CLINICAL RELEVANCE
CT-10.4	CRITERIA FOR LABORATORY VALUES OF POTENTIAL CLINICAL RELEVANCE REVISED
CT-11.1	LISTING OF VITAL SIGNS OF POTENTIAL CLINICAL RELEVANCE BY SUBJECT
CT-11.2	CRITERIA FOR POTENTIALLY CLINICALLY RELEVANT VITAL SIGN ABNORMALITIES
CT-12.1	LISTING OF ECG MEASUREMENTS OF POTENTIAL CLINICAL RELEVANCE
CT-12.2	CRITERIA FOR ECG MEASUREMENTS OF POTENTIAL CLINICAL RELEVANCE
CT-12.3	ECG DIAGNOSIS MAPPING FOR ECG MEASUREMENTS OF POTENTIAL CLINICAL RELEVANCE
CT-13.1.1	INCIDENCE OF LABORATORY VALUES OF POTENTIAL CLINICAL RELEVANCE
CT-13.1.2	INCIDENCE OF POTENTIALLY CLINICALLY RELEVANT SHIFTS IN LIPIDS
CT-13.1.3	INCIDENCE OF POTENTIALLY CLINICALLY RELEVANT SHIFTS IN GLUCOSE
CT-13.1.4	INCIDENCE OF LABORATORY VALUES OF POTENTIAL CLINICAL RELEVANCE REVISED
CT-13.2.1	LABORATORY TEST RESULTS FOR SERUM CHEMISTRY - MEAN CHANGE FROM BASELINE
CT-13.2.2	LABORATORY TEST RESULTS FOR HEMATOLOGY - MEAN CHANGE FROM BASELINE
CT-13.2.3	LABORATORY TEST RESULTS FOR URINALYSIS - MEAN CHANGE FROM BASELINE

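### SAP 5.5.2 and Table CT-13.2.1 do not limit mean changes in glucose, lipids and insulin to fasting samples, so non-fasting values not replaced by a same-visit repeat are pooled with fasting ones

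*SAP*

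**What the plan says.** SAP 5.5.2 describes the laboratory means as "Summary statistics (frequency, mean, standard deviation, minimum, and maximum) for the clinical laboratory measurements at all scheduled visits, and changes from baseline". Appendix 4 implements this for chemistry as CT-13.2.1, titled "LABORATORY TEST RESULTS FOR SERUM CHEMISTRY - MEAN CHANGE FROM BASELINE". Neither mentions fasting.

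Fasting does appear in the incidence analyses. SAP 5.5.2 plans the "incidence of treatment-emergent clinically relevant changes in fasting lipid parameters and glucose", defined in Table 5.5.2-1. SAP Appendix 1 sets glucose limits of 115 mg/dL fasting and 200 mg/dL non-fasting, and its lipid limits are for fasting values. Insulin, which the protocol lists under serum chemistry (Table 3.6.3.2-1), has no fasting criterion anywhere in the SAP.

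Protocol 3.6.3.2 states the basic rule: "Subjects should be fasting for a minimum of 10 hours prior to any blood draws for assessment of safety, including baseline". It then provides for lapses: "If a nonfasting blood sample is initially obtained and the test results possibly impacted, a fasting blood sample should be drawn shortly afterwards", with the affected tests repeated.

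On repeats, SAP 5.5.2 says: "If laboratory tests assessments are repeated for the same visit, the last repeated values are used for summary tables". This is done by "sorting patient data by visit date and visit time (if applicable) within the same visit identification".

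**The concern.** Glucose, triglycerides and insulin depend on whether the subject has eaten. The SAP recognises this for its shift table and for the glucose limits in Appendix 1, but not for the means. Two analyses of the same analytes could therefore rest on different sets of samples, with nothing in the tables to show it.

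Long-term safety is the secondary objective, and Protocol 1.3 discusses hyperglycaemia as a concern for atypical antipsychotics. There is one arm, so no control group would offset a change over time in the mix of fasting and non-fasting samples. If that mix changed between the Trial 248 Week 52 baseline and the later annual visits, part of the reported mean change would come from the mix and not from the subjects' metabolism.

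**Working it through.** The documents give no figure to reproduce: no sample-size calculation, no rate of fasting compliance, and no fasting to non-fasting difference. The check has two parts.

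**Which value reaches the mean**

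- Fasting sample at the visit: it is used.
- Non-fasting sample with a fasting redraw under the same visit identification: the redraw replaces it.
- Non-fasting sample, no redraw: the non-fasting value is used. This can happen because the redraw is worded as a recommendation and depends on a judgement: "If a nonfasting blood sample is initially obtained and the test results possibly impacted". The separate fasting confirmation in footnote b of Protocol Table 3.6.3.2-1 applies only to glucose of 125 mg/dL or more, before HbA1c testing.
- Non-fasting sample, redraw filed under another visit (for example, unscheduled): not settled. The repeat rule works within one visit identification, and the means use scheduled visits, which would leave the first value in. SAP 5.1.3, however, maps assessments to months by trial day (Month 12 is days 348–379), so a prompt redraw could fall in the same month. The SAP does not say which rule governs.
- Non-fasting baseline sample, redrawn some days later: not settled either. Baseline is the last Trial 248 visit with data (SAP 5.1.2), the first Study 270 injection is given at that visit (Protocol 3.6.1.1), and the month windows begin at day 16.

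**How large the effect could be**

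Let D be the mean non-fasting minus fasting difference, f the share of visits whose first sample is non-fasting, and r the share of those replaced by a same-visit fasting repeat (taken as equal at baseline and later). The pooled mean at a visit exceeds the fasting mean by D × f × (1 − r), so:

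bias in mean change = D × (f_later − f_baseline) × (1 − r)

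Every input is an assumption: f_baseline = 5%; f_later = 10% to 25%; D = 10 to 30 mg/dL for glucose and 20 to 60 mg/dL for triglycerides.

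With r = 0:

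- Glucose: 10 × (0.10 − 0.05) = 0.5 to 30 × (0.25 − 0.05) = 6.0 mg/dL.
- Triglycerides: 20 × 0.05 = 1 to 60 × 0.20 = 12 mg/dL.

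| Share replaced (r) | Glucose, mg/dL | Triglycerides, mg/dL |
|---|---|---|
| 0 | 0.5 to 6.0 | 1 to 12 |
| 50% | 0.25 to 3.0 | 0.5 to 6.0 |
| 90% | 0.05 to 0.6 | 0.1 to 1.2 |
| 100% | 0 | 0 |

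If f is the same at both times, the bias is 0 for any r. If compliance improves, from 15% non-fasting to 5% with r = 0, the bias is −0.10 × D: −1 to −3 mg/dL for glucose and −2 to −6 mg/dL for triglycerides.

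For scale, assume SDs of change of 15 and 50 mg/dL. The standard error of a mean change is 15/√500 = 0.67 and 50/√500 = 2.24 mg/dL with 500 paired subjects, the low end of anticipated enrolment. It is 15/√100 = 1.5 and 50/√100 = 5.0 mg/dL with 100. At 90% replacement the bias is below one standard error throughout. With no or half replacement, the upper ends (6.0 and 12; 3.0 and 6.0) exceed it at either n.

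No size is offered for insulin or cholesterol, because no D was assumed for them.

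**The case against.** A reader might infer that the mean tables take every scheduled sample regardless of fasting, so that any drift in compliance would show up as metabolic change. The documents do not support this. Fasting is the stated default for every safety draw, baseline included. A sample that may be affected should be redrawn, and a redraw under the same visit replaces it. Nor can it be said that an unscheduled redraw is necessarily lost: that depends on how redraws are labelled, which the documents do not say, and the day mapping in SAP 5.1.3 may bring it back in.

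The bias also needs the residual non-fasting share to change over time, and nothing in the documents shows that it does. The tables are descriptive, so no test or decision rule depends on them. Glucose and lipids are also covered by fasting-based shift tables (CT-13.1.2 and CT-13.1.3), the Appendix 1 limits and the related adverse-event tables. Fewer subjects will have a late paired sample than enrolled, so a standard error at n = 500 makes any bias look larger relative to noise than it would be at late visits.

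All of this stands, and it limits the point to values that are not redrawn or whose redraw is not assigned to the visit. It does not remove the point. The fasting rule is a recommendation, the redraw turns on judgement, and the SAP plans for non-fasting glucose values without saying what the means do with them. A descriptive mean can still be biased. Insulin has no fasting-specific analysis to fall back on.

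**Conclusion.** The point holds as a gap in specification: the means for glucose, lipids and insulin are neither restricted to fasting samples nor split by fasting status, and residual non-fasting values are pooled. The consequence is conditional. On the assumed inputs it runs from about 6 mg/dL for glucose and 12 mg/dL for triglycerides with no redraws down to 0.6 and 1.2 mg/dL or less at 90% replacement. It is zero if the residual share is stable and negative if compliance improves. These figures also assume that D and r are the same at both times.

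It would go too far to conclude that a rise in CT-13.2.1 must be an artefact, or that the means will be biased upward; the documents contain no compliance data in either direction. This is a cheap improvement.

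**What to change.** In SAP 5.5.2 and CT-13.2.1:

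- Summarise glucose, total, LDL and HDL cholesterol, triglycerides and insulin only from samples recorded as fasting at both baseline and the visit in question.
- Assign a fasting redraw made because the scheduled sample was non-fasting to that scheduled visit, including baseline, and state that this takes precedence over the visit-identification and day-window rules.
- Footnote the number of non-fasting samples excluded at each visit.

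The fasting-mix term is then zero by construction, and the means use the same kind of sample as the shift table. The cost is a few sentences and a programming filter. No new data should be needed, since the fasting-only shift table and the two glucose limits already presuppose a recorded fasting status. The downside is a smaller n for these analytes, of a size the documents do not allow to be computed.

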	Borderline 200~<240	High >=240
	Normal/Borderline <240	High >=240
	Normal <200	Borderline/High >=200
	Any Value	Increased >=40
LDL Cholesterol(mg/dL), fasting		
	Normal <100	High >=160
	Borderline 100~<160	High >=160
	Normal/Borderline <160	High >=160
	Normal <100	Borderline/High >=100
	Any Value	Increased >=30
HDL Cholesterol(mg/dL), fasting		
	Normal >=40	Low<40
	Any Value	Decreased >=20
Triglycerides(mg/dL), fasting		
	Normal <150	High >=200
	Normal <150	Very High >=500
	Borderline 150~<200	High >=200
	Borderline 150~<200	Very High >=500
	Normal/Borderline <200	High >=200
	Normal/Borderline <200	Very High >=500
	Normal <150	Borderline/High/Very High >=150
	Normal/Borderline /High >=200	Very High >=500
	Any Value	Increased >=40
Glucose(mg/dL), fasting		
	Normal <100	High >=126

Parameters	Baseline	Post-baseline
	Impaired Fasting Glucose 100~<126	High $\geq 126$
	Normal/ Impaired Fasting Glucose <126	High $\geq 126$
	Any Value	Increased $\geq 10$

Note: The National Cholesterol Education Program (NCEP) Adult Treatment Program Classifications of lipids (refer to fasting lipid measurements) are used for lipid parameters and the American Diabetes Association Criteria are used for glucose.

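### SAP Table 5.5.2-1: the baseline bound in the triglyceride row for Normal/Borderline/High shifting to Very High contradicts its own label; the table's bands give <500 mg/dL, not >=200

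*SAP*

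**What the plan says.** SAP Section 5.5.2 commits to reporting the "incidence of treatment-emergent clinically relevant changes in fasting lipid parameters and glucose" for the safety sample, with the changes defined by Table 5.5.2-1. Each category row pairs a baseline range with a post-baseline range.

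The triglyceride block (fasting, mg/dL) has these bands:

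- Normal: <150
- Borderline: "Borderline 150~<200"
- Normal and Borderline pooled: "Normal/Borderline <200"
- High: >=200
- Very High: "Very High >=500"

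The row in question has the baseline cell "Normal/Borderline /High >=200" and the post-baseline cell "Very High >=500".

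The comparable pooled baseline cells elsewhere in the table are "Normal/Borderline <240" (total cholesterol), "Normal/Borderline <160" (LDL cholesterol) and "Normal/ Impaired Fasting Glucose <126" (glucose). SAP Appendix 4 reports the lipid shifts in table CT-13.1.2.

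**The concern.** A category that includes Normal and Borderline cannot start at 200 mg/dL, because both bands lie entirely below 200. A range open above 200 also contains Very High, which the label does not name and which is the row's destination. The label and the number therefore describe different sets of subjects, and the SAP has no explicit rule on which governs.

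What is at stake is the meaning of treatment-emergent in this row:

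- **Subjects already at 500 or above.** Under the printed number they count as shifting to Very High if they stay there, or even if they fall but remain at or above 500. Such baselines are possible: the numeric laboratory exclusions in the protocol (Table 3.4.3-1, criterion 9) contain no triglyceride limit, so only the investigator's judgement would keep these subjects out.
- **High-to-Very-High shifts.** The table has no separate row for them. Under the printed number they are mixed with subjects who stayed Very High, and the two cannot be separated within the table. With a bound of <500, subtracting the <200 to >=500 row would isolate them.

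Two programmers could each follow part of the cell and produce different counts.

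**Working it through.** **1. Bound implied by the label.** Using the table's own bands, and ending High where Very High begins:

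Normal (<150) + Borderline (150 to <200) + High (200 to <500) = <500 mg/dL.

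The printed bound is >=200. The label includes 0 to <200 and the printed bound does not. The printed bound includes 500 and above and the label does not. They agree only on 200 to <500.

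**2. The table's own convention.** The other pooled baseline rows that shift to the next category up use the post-baseline cut as the baseline ceiling:

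| Parameter | Baseline | Post-baseline |
|---|---|---|
| Total cholesterol | <240 | >=240 |
| LDL cholesterol | <160 | >=160 |
| Triglycerides, Normal/Borderline | <200 | >=200 |
| Glucose | <126 | >=126 |
| Triglycerides, Normal/Borderline/High, as printed | >=200 | >=500 |

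The same convention gives <500 to >=500 for the last row.

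**3. Overlap check.** Leaving out the five Any Value rows, there are 4 (total cholesterol) + 4 (LDL) + 1 (HDL) + 8 (triglycerides) + 3 (glucose) = 20 category-shift rows. In 19 the baseline and post-baseline ranges are disjoint, so an unchanged value cannot count as a shift. In this one both ranges contain every value from 500 upward.

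**4. Worked cases.**

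| Baseline to post-baseline | Counted by printed number | Counted by label | Meets another triglyceride category row |
|---|---|---|---|
| 120 to 510 | no | yes | yes |
| 180 to 510 | no | yes | yes |
| 300 to 510 | yes | yes | no |
| 600 to 600 | yes | no | no |
| 800 to 520 | yes | no | no |

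**5. Size, under assumptions only.** The documents give no triglyceride distribution. For illustration, assume log-normal values with median 120 to 160 mg/dL, log-scale SD 0.45 to 0.65, within-subject correlation 0.5 to 0.7, one post-baseline value, and 500 to 800 subjects (the anticipated enrolment in SAP Section 4). With z(x) = [ln x − ln median]/SD, and baseline and post-baseline bivariate normal on the log scale:

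- P(baseline >=500 and post >=500) runs from 0.0037% (median 120, SD 0.45, correlation 0.5) to 1.475% (median 160, SD 0.65, correlation 0.7).
- Expected subjects wrongly added: from 500 × 0.000037 = 0.02 to 800 × 0.01475 = 11.8.
- Row total by printed number over row total by label, P(baseline >=200, post >=500) / P(baseline <500, post >=500): 0.79 to 1.49.
- Subjects wrongly omitted, P(baseline <200, post >=500): up to about 6.5 of 800.

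These are not bounds. If any of several post-baseline values can trigger the shift, the top scenario rises to about 20 of 800 with three values and about 23 with five (simulation, equal correlation between all pairs of values).

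**The case against.** The strongest reply is that nobody would program the number literally. The note under the table says the lipid rows use the NCEP classification, and the section text and table title speak of treatment-emergent changes. A subject already Very High cannot newly become Very High, so both point to the label. This is fair, and it makes literal programming less likely. It does not correct the cell, and a shift table is normally programmed from its printed bounds.

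Second, the consequence is small. This is one descriptive row among 25 in a single-arm trial with no formal testing. Subjects moving from below 200 to 500 or more still appear in other triglyceride rows, a change from 300 to 510 also meets the Any Value increase of >=40, and individual values can be traced in listings CT-10.1 and LAB-1. All of this stands and sets the severity.

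Third, the illustrative counts rest on inputs from outside the documents, span a factor of about 600, and take planned enrolment as if every subject had paired fasting values. That also stands. The finding rests on the band comparison and does not need the counts.

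Fourth, <500 is not printed anywhere in the table, and a High-only row may have been intended, since none exists. That is plausible, so the sponsor should confirm the intent. On either reading the printed cell is wrong and lacks an upper limit of 500. A fault in reading the PDF is an unlikely explanation, because both the sign and the number would have to be misread while the neighbouring cells are clean.

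**Conclusion.** The concern holds. The baseline cell contradicts its own label, and it is the only category-shift row of the table in which an unchanged value can count as a shift. That rests on the table alone.

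Of the four baseline bands that can pair with a post-baseline value of 500 or more, the label and the number agree only on High. The number adds Very High, and the label adds Normal and Borderline. Neither the size nor the direction of the effect on the row total can be determined from the documents. The harm arises only if the printed number is programmed, and the documents do not show the program. No test, sample size or endpoint conclusion depends on the row. Severity is minor.

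**What to change.** Change the baseline cell to Normal/Borderline/High <500, which matches the label and the convention of the other pooled next-category rows. If the sponsor confirms that a High-only row was intended, change both label and bound to High 200~<500. Then check that the CT-13.1.2 program applies the corrected bound.

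The cost is one table-cell correction in the SAP and one program check. No new data are needed.
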